 - Have the VentaProst dose reduced to the previous dose level (after the VentaProst dose has stabilized) at which one or more hemodynamic parameter showed maximum improvement. The VentaProst dose level will remain at this setting until clinical conditions determine the need for changing the dose.

Arterial and central venous blood oxygenation parameters will also be considered in the titration process.

Patients requiring post-operative support with epoprostenol will be allowed to continue on VentaProst treatment in the ICU as long as they are still on mechanical ventilation. For weaning, doses will be decreased in increments of 20% of the VentaProst equivalent dose, with a minimum of 30 minutes between changes, down to 20% of the dose before discontinuation (see Weaning Guideline from Part I above).

	
VentaProst weaning will occur from mechanical ventilation only. If the patient is extubated and placed on institution's standard of care delivery system for administering aerosolized Veletri, weaning from aerosolized Veletri will follow each institution's guideline.
 
Hemodynamic, oxygenation, and ventilator parameters will be obtained before and at 15 to 30 minutes after each VentaProst dose change to demonstrate the effect of the changes. Final measurements will be collected 15 to 30 minutes after discontinuation of VentaProst.

Number/Type of Patients	
Approximately 10 patients will be enrolled in each part of this study. A minimum of three patients at an individual site will be enrolled in Part I of the study before the site can continue to Part II.

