¹¹ For those patients with presence or history of significant restrictive or obstructive lung disease

¹² Vital signs and weight only

Table 2 – Schedule of Assessments and Procedures – Part II

Study Procedures	Screening	Intra-Operative	VentaProst Treatment Period (OR/ICU)	End of Study
Written Informed Consent	X			
Demographics	X			
Assign Patient ID	X			
Medical History	X			
Medication History	X			
Physical Examination	X			X
Vital Signs/Weight/Height	X			X ⁹
12-Lead ECG	X			X
Spirometry	X ⁸			
Clinical Laboratory Sampling	X			X
Serum Pregnancy Test	X			X
Inclusion/Exclusion Criteria	X	X		
Cardiac Surgery with CPB		X		
Administer VentaProst			X ⁶	
Hemodynamic Parameters ¹		X ⁵	X ⁷	
Oxygenation Measurements ²			X ⁷	
Ventilator Parameters ³			X ⁷	
AE Monitoring ⁴		X		X
Concomitant Medications	X	X		X

¹ Hemodynamic parameters include, but not limited to, Cardiac Index (CI), Cardiac Output (CO), Central Venous Pressure (CVP), Diastolic Pulmonary Arterial Pressure (dPAP), Diastolic Systemic Arterial Pressure (dSAP), Heart Rate (HR), Mean Pulmonary Arterial Pressure (mPAP), Mean Systemic Arterial Pressure(mSAP), Pulmonary Capillary Wedge Pressure (PCWP), Pulmonary Vascular Resistance (PVR), Rhythm, Systolic Pulmonary Arterial Pressure (sPAP), and Systolic Systemic Arterial Pressure (sSAP)

² Oxygenation measurements include SaO₂ or SpO₂ and PaO₂

³ Ventilator parameters include Ventilator Type, Ventilator Mode, FiO₂, Inspiratory Time, Mean Airway Pressure, Peak Inspiratory Pressure, Positive End Expiratory Pressure, and Respiratory Rate

⁴ To include unanticipated medical events in the judgment of the investigator

⁵ Measure hemodynamic parameters prior cardiac surgery with CPB. Prior to dosing with VentaProst, measure hemodynamic, oxygenation, and ventilator parameters

⁶ Initiate VentaProst at a starting dose of 3.4 ng/kg/min of VentaProst and titrate VentaProst dose up in 3.4 ng/kg/min increments as clinically indicated (refer to VentaProst Pharmacy Manual); stabilize the patient on final dose of VentaProst

⁷ Measure hemodynamic, oxygenation, and ventilator parameters before and after each VentaProst dose change (during dosing, stabilization, and weaning [if still intubated] and at 15 to 30 minutes after discontinuation of VentaProst

⁸ For those patients with presence or history significant restrictive or obstructive lung disease

⁹ Vital signs and weight only

TABLE OF CONTENTS

INVESTIGATOR'S SIGNATURE PAGE	3
1. CLINICAL PROTOCOL SYNOPSIS.....	4

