4.2 Part II

The second part of the study will be conducted in approximately 10 consented cardiothoracic surgical patients on CPB with perioperative pulmonary hypertension (mPAP > 25 mm Hg). This part of the study is designed to establish a dose response relationship of VentaProst to PD effect by dose escalation in these patients. The goal will be to determine the VentaProst dose necessary to achieve at least a 15% improvement in one or more hemodynamic parameters (as defined by the clinical team).

Hemodynamic measurements will be taken prior cardiac surgery (after induction) with CPB, prior to dosing with VentaProst, and after each dose titration step.

Qualifying patients will:

- Receive a starting dose of 3.4 ng/kg/min of VentaProst
- Have hemodynamic parameters monitored and recorded
- Receive increase in the VentaProst dose in 3.4 ng/kg/min increments (refer to VentaProst Pharmacy Manual)
 - *IF A GREATER THAN A 15% IMPROVEMENT IN ONE OR MORE HEMODYNAMIC PARAMETERS (AS DEFINED BY THE CLINICAL TEAM) IS SEEN WITH THE INITIAL VENTAPROST DOSE, but NO additional clinically meaningful change is seen with this first dose escalation:*
 - Have the VentaProst dose reduced to the initial dose level
 - *IF A GREATER THAN A 15% IMPROVEMENT IN ONE OR MORE HEMODYNAMIC PARAMETERS (AS DEFINED BY THE CLINICAL TEAM) IS SEEN WITH THE INITIAL VENTAPROST DOSE, but AN additional clinically meaningful change is seen with the first dose escalation:*
 - Continue to receive VentaProst in increasing steps of 3.4 ng/kg/min every 5 to 15 minutes as clinically indicated until no further improvements in one or more hemodynamic parameters are achieved or until dose-limiting pharmacological effects are elicited or a tolerance limit to VentaProst is established.

- *IF A LESS THAN A 15% IMPROVEMENT IN ONE OR MORE HEMODYNAMIC PARAMETERS (AS DEFINED BY THE CLINICAL TEAM) IS SEEN WITH FIRST DOSE INCREASE:*
 - Continue to receive VentaProst in increasing steps of 3.4 ng/kg/min every 5 to 15 minutes as clinically indicated until no further improvements in one or more hemodynamic parameters are achieved or until dose-limiting pharmacological effects are elicited or a tolerance limit to VentaProst is established.

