 - Reduce the VentaProst dose to the previous dose level (after the VentaProst dose has stabilized) at which the one or more hemodynamic parameters showed maximum improvement. The VentaProst dose level will remain at this setting until clinical conditions determine the need for changing the dose.

Arterial and central venous blood oxygenation parameters will also be considered in the titration process.

Hemodynamic, oxygenation, and ventilator parameters will be obtained at the time of each VentaProst dose adjustment in the ICU.

Patients requiring post-operative support with epoprostenol will be allowed to continue on VentaProst treatment in the ICU as long as they are still on mechanical ventilation. For weaning, doses will be decreased in increments of 20% of the VentaProst equivalent dose, with a minimum of 30 minutes between changes, down to 20% of the dose before discontinuation (see Section 4.1, Weaning Guideline in Part I above). If the patient is extubated and placed on institution's standard of care delivery system for administering aerosolized Veletri, weaning from aerosolized Veletri will follow each institution's guideline.

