10.2.3 VentaProst Treatment (OR/ICU)

10.2.3.1 Dosing

The patient will undergo the following study-related procedures and evaluations:

- Patients will receive a starting dose of 3.4 ng/kg/min of VentaProst
- Patients will receive increases in VentaProst dose by 3.4 ng/kg/min (refer to VentaProst Pharmacy Manual)
 - If greater than a 15% improvement in one or more hemodynamic parameters (as defined by the clinical team) is seen with the initial VentaProst dose, but NO additional clinically meaningful change is seen with the first dose escalation, the VentaProst dose will be reduced to the initial dose level
 - If greater than a 15% improvement in one or more hemodynamic parameters (as defined by the clinical team) is seen with the initial VentaProst dose, but AN additional clinically meaningful change is seen with the first dose escalation, continue to dose with VentaProst in increasing steps of 3.4 ng/kg/min every 5 to 15 minutes as clinically indicated until no further improvements in one or more hemodynamic

parameters are achieved or until dose-limiting pharmacological effects are elicited or a tolerance limit to VentaProst is established

- If less than a 15% improvement in one or more hemodynamic parameters (as defined by the clinical team) is seen with first dose increase, continue to dose with VentaProst in increasing steps of 3.4 ng/kg/min every 5 to 15 minutes as clinically indicated until no further improvements in one or more hemodynamic parameters are achieved or until dose-limiting pharmacological effects are elicited or a tolerance limit to VentaProst is established. After the VentaProst has been stabilized, reduce the VentaProst dose to the previous dose level at which a hemodynamic parameter showed maximum improvement. The VentaProst dose level will remain at this setting until clinical conditions determine the need for changing the dose
- Measure hemodynamic, oxygenation, and ventilator parameters at each dose adjustment
- Record all concomitant medications
- Record AEs

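### Part II up-titration may step every 5 minutes, but the synopsis reads 15 to 30 minutes after each dose change and the other sections give no time, so a reading can be assigned to the wrong dose

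*Combined protocol and SAP*

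**What the plan says.** Section 4.2 describes Part II as "designed to establish a dose response relationship of VentaProst to PD effect by dose escalation in these patients". The step rule there is "Continue to receive VentaProst in increasing steps of 3.4 ng/kg/min every 5 to 15 minutes as clinically indicated until no further improvements" are seen, or until an effect or tolerance limit is reached. The synopsis and Section 10.2.3.1 give the same interval.

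The time of the reading is stated in five ways:

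- Synopsis, Study Design, Part II: readings are "obtained before and at 15 to 30 minutes after each VentaProst dose change to demonstrate the effect of the changes".
- Table 2, footnote 7: "Measure hemodynamic, oxygenation, and ventilator parameters before and after each VentaProst dose change". It covers dosing, stabilization and weaning, and attaches 15 to 30 minutes only to discontinuation.
- Section 4.2, hemodynamics: "prior to dosing with VentaProst, and after each dose titration step".
- Section 4.2, ICU: "parameters will be obtained at the time of each VentaProst dose adjustment in the ICU".
- Section 10.2.3.1: "Measure hemodynamic, oxygenation, and ventilator parameters at each dose adjustment".

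Table 2, footnote 6 adds an instruction to "stabilize the patient on final dose of VentaProst", with no duration. Section 10.2.3.2 gives the 15-to-30-minute window and a 15-minute stabilization for weaning, where steps are at least 30 minutes apart.

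**The concern.** A dose-response curve needs each reading tied to one dose and taken at a comparable time on that dose. These rules secure neither. The synopsis window is longer than most of the permitted step intervals. The wording in Sections 4.2 (ICU) and 10.2.3.1 does not say whether a reading taken at an adjustment belongs to the outgoing or the incoming dose, which are 3.4 ng/kg/min apart.

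The possible errors run in opposite directions. A late reading credited to the dose that started the clock makes that dose look too effective if escalation has continued. A reading taken before the effect has settled makes its dose look too weak, so the dose labelled as giving a 15% improvement comes out too high. The clinician chooses the interval, so time on dose can differ between patients and between steps of one patient, and the shape of the curve is then mixed with timing.

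**Working it through.** The plan states no figure of its own to reproduce. The check has two parts.

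**1. Do the step interval and the window fit together?**

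Inputs: steps of 3.4 ng/kg/min every 5 to 15 minutes (Section 4.2); window of 15 to 30 minutes (synopsis). Further steps possible before the reading = time of reading / step interval, counting a step due at that moment.

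- 5-minute steps: 15/5 = 3 and 30/5 = 6 steps, which is 3 × 3.4 = 10.2 to 6 × 3.4 = 20.4 ng/kg/min above the dose being assessed.
- 15-minute steps: the window opens as the next step falls due, so only a reading at minute 15, before that step, belongs to the right dose.

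**2. If the window is for weaning only, what does a 5-minute reading show?**

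Inputs from Section 2.1: half-life 2.7 minutes (animal data) or about 3 minutes (in vivo); steady state in animal infusions within 15 minutes. The documents give no half-life for the hemodynamic effect. I assume that effect follows first-order accumulation with half-life h, and I take 1 to 5 minutes as a range.

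- Share of a first dose's steady state at time t: 1 − r, where r = 2^(−t/h).
- Lag behind the nominal dose, in steps, with equal intervals: D(n) = (D(n−1) + 1) × r, which settles at r/(1 − r).

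For t = 5 and h = 2.7, r = 0.277, the share is 0.723 and the lag is 0.277/0.723 = 0.383 step. For h = 3, r = 0.315, the share is 0.685 and the lag is 0.460 step.

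| h (min) | Share at 5 / 10 / 15 min | Settled lag in steps, 5- / 10- / 15-min intervals |
|---|---|---|
| 1 | 97% / 99.9% / 100% | 0.03 / 0.001 / under 0.001 |
| 2.7 | 72% / 92% / 98% | 0.38 / 0.08 / 0.02 |
| 3 | 69% / 90% / 97% | 0.46 / 0.11 / 0.03 |
| 5 | 50% / 75% / 88% | 1.00 / 0.33 / 0.14 |

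In dose terms, the 5-minute lag is 0.383 × 3.4 = 1.3 or 0.460 × 3.4 = 1.6 ng/kg/min on the documents' half-lives.

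Mixed intervals alter the apparent shape. Take a truly linear response and L(n) = n − (n − L(n−1)) × r. With h = 2.7, a 15-minute step followed by a 5-minute step gives L(1) = 0.979 and L(2) = 2 − 1.021 × 0.277 = 1.717. The second increment is 0.738, or 75% of the first (73% for h = 3; 97% to 64% for h from 1 to 5). In the reverse order it reads 173% of the first (186% for h = 3; range 106% to 262%).

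**The case against.** A reader might infer that Part II sets no minimum time on dose for up-titration at all. The documents do not support that as a flat statement. The synopsis sentence refers to each dose change, does not limit itself to weaning, and treats discontinuation separately. In Part I, Table 1 footnotes 9 and 10 pair 15-minute steps with the same window and say it applies during dosing, so the sponsor does use it for up-titration. Against that, the Part II sentence follows the weaning text, Section 10.2.3.2 places the window in weaning, and Table 2 footnote 7 drops it for dose changes. The sentence is ambiguous. Read one way it conflicts with short steps; read the other way up-titration has no time.

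A reader might also infer that 5-minute steps spoil the dose response. That is not shown. The half-life of 2.7 minutes and the steady-state time come from animals, the drug here is inhaled for local effect, and a 15-minute ceiling does not exclude faster onset. A full-step lag needs the 5-minute end of my assumed range. Uniform 5-minute steps do not by themselves create a false plateau.

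Two further points stand. The reading before each change, in the synopsis and footnote 7, already belongs to one dose, and the plan asks for stabilization before the final dose is settled. But no duration is given, and stabilizing the final dose does not cover the lower doses that form the curve. Also, the Pharmacy Manual and the Appendix 2 schematic are not in the text available, and Section 12.1 leaves the SAP to be developed. The finding is therefore about the stated rules, and does not claim that timing is absent from every trial document.

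**Conclusion.** The concern holds as a conflict between stated rules, in the part of the study designed to establish the dose response. If the synopsis window covers up-titration, only a 15-minute step read at minute 15 complies, and with 5-minute steps the reading can fall 10.2 to 20.4 ng/kg/min above its dose. This result needs no pharmacological assumption. If the window is for weaning only, readings may come at 5 minutes. The lag is then 0.38 to 0.46 of a step on the documents' half-lives, and from negligible to one step over 1 to 5 minutes, provided effect follows first-order accumulation.

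The stakes are moderate. Part II is descriptive in about 10 patients, and Part I and the primary endpoint are unaffected. A mandatory longer step does not follow from this, because Section 2.1 makes rapid optimization of the dose an aim of Part II.

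**What to change.** Put one rule in the synopsis, Table 2 footnote 7, Section 4.2 (both sentences) and Section 10.2.3.1. The dose-response reading for each dose is taken immediately before the next change and assigned to the dose then running. The 15-to-30-minute window applies to weaning, to discontinuation and to any dose held at least 15 minutes. Keep 5-minute steps where clinically indicated.

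Record the time of every pump-rate change and every reading. Section 6.3.1 already logs the time of dose administration but does not mention rate changes. In the SAP, pre-specify a sensitivity analysis of the Part II dose response restricted to readings at or beyond one fixed time on dose, for example 10 minutes, with the cut-off set before database lock.

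The cost is small: harmonized wording, time fields if the eCRF lacks them, and one SAP paragraph. The restricted analysis will have fewer readings and may be selective, because the clinician chooses how long to stay on a dose. It should be read beside the full analysis and should not replace it.

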4.3 Duration of Participation

Patients who meet entry criteria will be entered into the study and the duration of study participation for each patient is listed below.

4.3.1 Part I

Individual patient participation is expected to be approximately 5 weeks including:

- Screening: up to 30 days
- Intra-Operative: 3-8 hours
- Aerosolized Veletri Treatment administered in accordance with each site's standard of care guidelines (OR/ICU): 24+ hours (dependent on multiple factors)
- VentaProst Treatment (ICU): 24+ hours (dependent on multiple factors)
- End of Study: 4+ hours (dependent on multiple factors)

4.3.2 Part II

Individual patient participation is expected to be approximately 5 weeks including:

- Screening: up to 30 days
- Intra-Operative: 3-8 hours
- VentaProst Treatment (OR/ICU): 24+ hours (dependent on multiple factors)
- End of Study: 4+ hours (dependent on multiple factors)

4.4 Screening

The purpose of Screening is to ensure that each patient meets all the specified inclusion and none of the exclusion criteria.

4.5 Intra-Operative/ICU

In Part I, approximately 10 cardiac surgery patients on CPB who meet entry criteria will be entered into the study and will receive conventionally-administered aerosolized Veletri (in accordance with each site's standard of care guidelines) in the OR or ICU. Once clinically defined hemodynamic effects are achieved in the ICU, the aerosolized epoprostenol will be stopped and patients will be crossed-over to a calculated VentaProst equivalent dose of 17 ng/kg/min. The VentaProst dose will then be increased in 20% increments (refer to VentaProst Pharmacy Manual) every 15 minutes to match the PD measures achieved with the aerosolized Veletri dose.

In Part II, approximately 10 cardiac surgery patients on CPB who meet study entry criteria will be entered into the study and will be assigned to receive a starting dose of 3.4 ng/kg/min of VentaProst in the OR or ICU. The VentaProst dose will then be increased in 3.4 ng/kg/min increments (refer to VentaProst Pharmacy Manual) every 5 to 15 minutes as clinically indicated until no further improvements in one or more hemodynamic parameters are achieved.

4.6 End of Treatment

In both Part I and Part II, final PD measurements (based on hemodynamic parameters, indices of oxygenation, and ventilator support) will be collected 15 to 30 minutes after discontinuation of VentaProst. End of study physical examination, vital signs/weight, 12-lead ECG, clinical laboratory testing, serum pregnancy testing, hemodynamic parameters, oxygenation measurements, ventilator parameters, adverse events monitoring, and concomitant medications will also be obtained at the end of treatment.

5. SELECTION AND WITHDRAWAL OF PATIENTS

Approximately 10 patients will be enrolled in each part of this study at approximately three clinical sites in the United States. A minimum of three patients at an individual site will be enrolled in Part I of the study before the site can continue to Part II.

Patients who do not meet all of the inclusion criteria or who meet any of the exclusion criteria will not be eligible to receive study medication.

5.1 Inclusion Criteria

Patients are eligible for this study if they meet all of the following criteria:

1. Women and Men 18 to 80 years of age
2. Provide written informed consent
3. Willing and able to comply with all aspects of the protocol
4. For patients in Part I:
 - a. Undergo cardiac surgery on CPB (including planned cardiac transplantation)
 - b. Clinically require treatment with and receive aerosolized Veletri
 - c. Demonstrate a clinically meaningful hemodynamic response to aerosolized Veletri (defined as at least a 15% improvement in one or more hemodynamic parameters [as defined by the clinical team])
5. For patients in Part II:
 - a. Undergo cardiac surgery with CPB (including planned cardiac transplantation)
 - b. Have perioperative pulmonary hypertension (mPAP > 25 mm Hg)
 - c. Clinically require treatment with inhaled epoprostenol

5.2 Exclusion Criteria

Patients are NOT eligible for this study if they meet any of the following criteria:

1. Current smoker (i.e., within the last 30 days)
2. Emergency operative status
3. Upper and/or lower respiratory tract infection within four weeks of screening
4. Contraindication to transesophageal echocardiogram (TEE) including esophageal disease or unstable cervical spine
5. Renal (creatinine > 2.0 mg/dL) or severe hepatic impairment
6. Thromboembolic disease treated with anticoagulant therapy
7. Bleeding disorders
8. Presence or history of significant restrictive or obstructive lung disease (FEV₁ and/or FVC < 60% of predicted normal lung function)
9. History of current malignancy or recurrence of malignancy within two years prior to Screening (not including patients with < 3 excised basal or squamous cell carcinomas)
10. History of a diagnosis of drug or alcohol dependency or abuse within one year
11. Recent history of stroke or transient ischemic attack (within six months prior to Screening) not due to trauma, repaired vascular malformation, or aneurysm
12. Significantly abnormal laboratory tests at Screening, including:
 - a. Alkaline phosphatase (AP), alanine aminotransferase (ALT, SGPT), aspartate aminotransferase (AST, SGOT), or total bilirubin > 2.5X of the

- upper limit of normal (ULN)
- b. Hemoglobin <9 gm/dL, white blood count (WBC) count <2500 mm³, neutrophil count <1500 mm³, platelet count <100 x 10³/mm³
- c. Evidence of hemoglobinopathy (including but not limited to sickle cell disease, thalassemia (all variants), hemoglobin M and variants with high oxygen affinity)

13. Pregnant or breastfeeding
14. Participation in an investigational drug, biologic, or investigational cardiac implant study within 30 days preceding the first dose of study medication or plans to take part in another investigational study within 30 days of study completion
15. Other severe, acute, or chronic medical or psychiatric condition or laboratory abnormality that may increase the risk associated with trial participation or investigational product administration or may interfere with the interpretation of trial results and, in the judgment of the Investigator or Sponsor, would make the patient inappropriate for entry into this trial
16. Any condition where aerosolized epoprostenol is contraindicated
17. Known allergy or sensitivity to epoprostenol, any of its ingredients, or the diluent (glycine)

